20.5 Insurance and compensation

The Sponsor has an insurance coverage for the treatment of participants in the event of injuries related to the clinical investigation, according to national regulations.

Participants will not receive payments for participation in the investigation. However, documented expenses such as travel and parking will be covered.

20.6 Financial Disclosure and Conflict of Interest

This study is initiated by and financed by Sponsor. Sites are reimbursed for all their expenses related to the study, including time and resources spent. Sponsor will provide all study devices and pay for all expenses related to the conduct of this study. Investigational sites and investigators with a financial interest in the outcome of the study will not be allowed to participate in the study as sites or investigators respectively.

21 Publication policy

Sponsor and Principal Investigators are committed to dissemination of study results. Results will not be withheld regardless of the findings.

The data and statistical analyses from Stage 1 and Stage 2 will be presented in scientific articles (one or more for each Stage) which will be submitted to a peer-reviewed journal in the field of headache, pain medicine or general neurology. Data and manuscripts will not be released before approval by Principal Investigators. All Principal Investigators will be listed as authors on abstracts and publications. All proposed publications and presentations resulting from or relating to the study (either from single sites or multiple sites) must be reviewed and approved by Sponsor before release. The clinical investigation will be pre-registered in the database clinicaltrials.org.

22 Bibliography

 Migraine induced by hypoxia: An MRI spectroscopy and angiography study. Brain 139, 723–737. https://doi.org/10.1093/brain/awv359
- Ashkanian, M., Gjedde, A., Mouridsen, K., Vafaee, M., Hansen, K.V., Østergaard, L., Andersen, G.,
 2009. Carbogen inhalation increases oxygen transport to hypoperfused brain tissue in
 patients with occlusive carotid artery disease. Increased oxygen transport to hypoperfused
 brain. Brain Res. 1304, 90–95. https://doi.org/10.1016/j.brainres.2009.09.076

# PAREMA1 Statistical Analysis Plan

# 1.1 Change log

| Version | Changes  |  |  |  |  |  |
|---------|--|--|--|--|--|--|
| 1.0     | NA   |  |  |  |  |  |
| 1.1     | The following changes were implemented prior to the interim analysis unblinding and readout:   |  |  |  |  |  |
|         | • Study power increased from 80% to greater than 85%.  |  |  |  |  |  |
|         | 
 
Minimum enrolment number increased from 174 to 200. Rationale for this change is
to increase study power.
 
  |  |  |  |  |  |
|         | • Maximum enrolment number increased from 220 to 240. Rationale for this change is to increase study power and decrease risk of not observing a true difference in the primary outcomes.   |  |  |  |  |  |
|         | • Figure 1 has been updated with the changes described above.  |  |  |  |  |  |
|         | • Addition of an additional exploratory analysis data set that includes the training attack. Rationale for this change is to investigate the effect of training.   |  |  |  |  |  |
|         | • The number of attacks per patient in the full data set will be estimated via a simulation using as its input the attack frequency observed in the interim data set (see Appendix for details).                                   |  |  |  |  |  |
|         | • The dropout percentage in the full data set will be estimated via a simulation using as its input the risk of dropout in a given week during the interim period (see Appendix for details).                                      |  |  |  |  |  |
|         | • It has been specified that trial site staff will not be informed of the final enrolment target found via the interim analysis. Rationale for this change is to reduce the risk of partial unblinding that could otherwise occur. |  |  |  |  |  |

# 1.2 Study Design

PAREMA1 is a randomized, controlled, double-blinded, parallel-group, group-sequential clinical study randomizing participants to either active or sham treatment, in a 1:1 ratio.

The clinical investigation will randomize at minimum 200 participants and at maximum 240.

In Stage 1 of the trial the participants will treat up to four attacks each. The first treated attack is a training attack and will not be used in the statistical analysis. All attacks reported after the training attacks are study attacks and will be used in the analysis. The reason for discarding the first attack is that it (cf. the pilot trial and post-market data) is not representative of normal use and effectiveness, the user having not yet become accustomed to correct use of the device.

# 1.3 Endpoints

The primary endpoint is absence of moderate or severe pain at 2 hours (AMSP2) which is an outcome that is valuable to patients and which has a good benefit risk/ratio when factoring in the low risk level of the treatment. The statistical power for AMSP2 in the study is above 95% (see section 1.5, below).

The study's most important secondary endpoint is Pain Freedom at 2 hours (PF2). Recognizing that this is the ideal outcome for patients, the study has been sized and designed with the aim of having a high statistical power for PF2.

# 1.4 Interim analysis procedure

After 60 subjects have provided data from at least one study attack in Stage 1, an interim analysis (IA) will be conducted. The IA will include all reported study attacks according to the ITT principle (see section 1.6 below).

Based on the data from the IA it will be decided how many additional patients to recruit into the study, and in turn how many patients will be included in total (N\_t). This decision will be taken according to the decision procedure flowchart shown in Figure 1:

[figure not shown]

Figure 1: Interim Analysis decision procedure

As shown in Figure 1, the interim analysis performs hypothesis tests for AMSP2 and PF2, using the O'Brien Fleming Spending function in which the significance thresholds of the p-value are respectively 0.0052 at the interim analysis and 0.048 in the full analysis.

The interim analysis will use the following assumptions:

- The observed AMSP2 and PF2 at the interim for both treatment arms
- The observed Intraclass Correlation based on the interim data set
- The number of attacks per patient in the full data set will be estimated via a simulation using as its input the attack frequency observed in in the interim data set (see Appendix for details).
- The dropout percentage in the full data set will be estimated via a simulation using as its input the risk of dropout in a given week during the interim period (see Appendix I for details).

As shown, the total number of included participants will be capped at 240 since this is the largest study that will be feasible to conduct.

The interim analysis does not include a criterion for early stopping due to effectiveness.

Staff involved in the conduct of the trial and closing enrolment will remain blind to the exact result of the interim analysis, but will be informed of the final enrolment target (N\_t). Study site staff will remain blind to the exact result of the interim analysis and final enrolment target (N\_t).

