16.3 Interim analysis

After 60 subjects have provided data from at least one study attack in Stage 1, an interim analysis (IA) will be conducted to re-estimate the study sample size. Based on the data from the IA it will be decided how many additional patients to recruit into the study. The IA will include two hypothesis tests on the interim data set, respectively of PF2 and AMSP2. These analyses will use the O'Brien Fleming Spending function in which the significance thresholds of the p-value are respectively 0.0052 at the IA and 0.048 in the full analysis. The IA will estimate the power for PF2 in the final analysis based on the observed PF2 rates in the trial thus far and re-estimate the study sample size accordingly. Regardless of the results of the IA, enrolment will continue to the originally estimated 174 subjects, and the total number of included participants will be capped at 220 since this is the largest study that will be feasible to conduct. The minimum number of participants in the study will be 174.

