### 1.5 Power and sample size calculation

#### 1.5.1 Assumptions

The estimated study size of 200 to 240 included participants has been determined on the basis of data from the pilot study (Fuglsang et al., 2018) and post-market data collected in Denmark, Sweden and Germany from 2018 to 2020.

To estimate the sample size for this trial, it was assumed that 12% of subjects in the sham group and 30% of subjects in the active group would experience PF2. For AMSP2, a 26% response rate in the sham group and a 61% response rate in the active group was assumed.

The primary statistical test for this analysis will be a  $\chi^2$  significance test adjusted for clustered data (using the methods of Donner and Banting (Donner and Banting, 1988)) since subjects could contribute more than one migraine attack. The intraclass correlation coefficient (ICC) from preliminary data on this device was 0.486. This is a group-sequential design with one interim analysis, so the O'Brien Fleming Spending function will be used to set significant thresholds of 0.0052 at the interim analysis and 0.048 at the final analysis.

Power and sample sizes were estimated via simulation using the above parameters for a  $\chi^2$  significance test adjusted for clustered data. These simulations assumed a third of subjects would have one migraine attack during the course of the study, a third of subjects would have two study attacks, and a third of subjects would have three study attacks. In the interim analysis, a more refined method of estimating number of attacks per participant will be employed, using the observed attack frequencies from the interim data (cf. section 1.4). Additionally, it was expected that 22% of subjects would drop out of the trial and 10% of attacks would have missing data at the 2 hour time point, for a total of 32% of randomized subjects that would not provide data usable for the statistical analysis of the primary or secondary endpoint.

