#### 1.7 Outcomes and Analysis

#### 1.7.1 Primary hypothesis

In line with earlier studies on aura-phase treatment (Bates D. et al., 1994; Olesen J. et al., 2004), the trial's **primary end point** will be absence of moderate or severe pain at 2 hours (AMSP2), ), i.e. the percentage of study attacks in which the participant reported absence of headache of moderate/severe intensity at 2 hours post-treatment initiation. "Study attacks" are all attacks treated and reported during Stage 1, apart from the first attack which is a training attack and is not included in the analysis.

The intention-to-treat (ITT) analysis set will be used for the primary effectiveness hypothesis test. The primary effectiveness hypothesis is:

 $H_0: p_{Rehaler} = p_{sham}$ 

 $H_a: p_{\text{Rehaler}} \neq p_{\text{sham}}$ 

Where:

pRehaler = proportion of attacks in the Rehaler group with AMSP2

psham = proportion of attacks in the sham group with AMSP2

The primary effectiveness hypothesis will be tested using a two-sided adjusted  $\chi^2$  test for clustered binary data (Donner and Banting, 1988) at a 5% level of significance.

If Pearson's chi-squared test statistic is written as  $\chi^2 = \sum_{i=1}^{G} \chi_i^2$  with G = the number of treatment groups, then the adjusted  $\chi^2$  approximately follows a chi-squared distribution with G-1 degrees of freedom and is calculated as follows (Donner and Banting, 1988):

$$\chi_A^2 = \sum_{i=1}^G \frac{\chi_i^2}{\overline{C_i}}$$

Where:

- $\overline{C}_{l} = \sum_{j=1}^{n_{i}} \frac{m_{ij}C_{ij}}{\sum m_{ij}}$
- $C_{ij} = 1 + (m_{ij} 1)\rho$
- G is the number of treatment groups
- ni is the number of individuals in group i
- ρ is the correlation coefficient between any two responses in the same individual
- mij denotes the number of observations for individual j in group i

The corresponding 95% confidence interval for the difference in proportion of attacks with AMSP2 between the Rehaler and sham groups will also be calculated as follows (Donner and Klar, 1993):

95% Confidence Interval:  $(\hat{p}_{Rehaler} - \hat{p}_{sham}) \pm 1.96 * \widehat{SE}(\hat{p}_{Rehaler} - \hat{p}_{sham})$ 

Where:

- $\hat{p}_{Rehaler}$  = observed proportion of attacks in the Rehaler group with AMSP2
- $\hat{p}_{sham}$  = observed proportion of attacks in the sham group with AMSP2

• 

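### The thresholds 0.0052/0.048 fit an interim look near 50% information and were not updated when the SAP raised N to 200–240, where the look falls at about 44% to 37%

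*SAP*

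**What the plan says.** SAP 1.4 places the interim at a subject count: "After 60 subjects have provided data from at least one study attack in Stage 1". It tests AMSP2 and PF2 there "using the O'Brien Fleming Spending function", and gives the cut-offs as "significance thresholds of the p-value are respectively 0.0052 at the interim analysis and 0.048 in the full analysis". SAP 1.5.1 says "This is a group-sequential design with one interim analysis" and repeats that the "Spending function will be used to set significant thresholds of 0.0052 at the interim analysis and 0.048 at the final analysis". Table 3 in SAP 1.7.3 lists the same pair for AMSP2 and PF2. Protocol 16.3 has the same trigger and the same pair, with the words "These analyses will use the O'Brien Fleming Spending function".

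Neither document states the information fraction at which the pair was computed, or which form of the spending function was used.

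Two further statements bear on how the pair is used. SAP 1.4 says that the interim has no criterion for stopping early for effectiveness. SAP 1.7.1 sets the primary test "at a 5% level of significance", whereas Table 3 uses 0.048 for the same test in the full data set.

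**The concern.** A spending function produces thresholds only once an information fraction is supplied. The trigger is fixed at 60 subjects, so the fraction falls as the planned total rises. SAP version 1.1 raised the minimum from 174 to 200 and the maximum from 220 to 240, but its change log lists no change to the thresholds. The stated pair should therefore no longer agree with the method that the SAP names.

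These are the pre-specified decision thresholds for the primary endpoint and the most important secondary endpoint. If they do not follow from the stated method, it is unclear which governs, the numbers or the method. The overall significance level also depends on a point that the SAP leaves open: whether an interim p-value below 0.0052 is itself a rejection.

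**Working it through.** **Inputs**
- Interim: 60 subjects with at least one study attack (SAP 1.4, protocol 16.3).
- Protocol minimum: 174 randomized, 30% without analyzable data (protocol 16.2).
- SAP version 1.1: 200 to 240 randomized (SAP 1.2), 32% not usable (SAP 1.5.1).
- Overall level 0.05, two-sided: "The primary effectiveness hypothesis will be tested using a two-sided adjusted" χ² test (SAP 1.7.1).

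**Information fraction t, by usable subjects**
- Protocol minimum: 174 × 0.70 = 122; t = 60/122 = 0.492.
- SAP minimum: 200 × 0.68 = 136; t = 60/136 = 0.441.
- SAP maximum: 240 × 0.68 = 163; t = 60/163 = 0.368.

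**Formulas**
The interim and final statistics are taken as bivariate normal with correlation √t. The O'Brien-Fleming-type (Lan-DeMets) spending function has two common forms for a two-sided test:
- 0.025 per side: interim two-sided p = 2 × [2 − 2Φ(2.2414/√t)].
- Applied once to two-sided 0.05: interim p = 2 − 2Φ(1.960/√t).

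The final threshold is the one that brings the overall level to 0.05. For any pair of critical values, overall alpha = 1 − P(|Z₁| ≤ c₁, |Z₂| ≤ c₂).

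**Reproducing the stated pair**
- Classical O'Brien-Fleming boundary, two equal looks (t = 0.5): constant 1.9774, which gives 0.00517/0.0480. This rounds to the stated pair.
- Applied-once form at t = 0.492: √t = 0.701, 1.960/0.701 = 2.795, which gives 0.0052, with 0.0479 at the final. This is also essentially the stated pair.
- Per-side form at t = 0.5: 0.0031/0.0490. This does not reproduce it.

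The pair is therefore consistent with a look near 50%, which is where the protocol's minimum sample size puts it.

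**Thresholds at the SAP's look**
At t = 0.441, √t = 0.664:
- Per side: 2.2414/0.664 = 3.37, so p = 0.0015.
- Applied once: 1.960/0.664 = 2.95, so p = 0.0032.

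At t = 0.368, √t = 0.607:
- Per side: 2.2414/0.607 = 3.69, so p = 0.0004.
- Applied once: 1.960/0.607 = 3.23, so p = 0.0012.

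| | t = 0.441 (N = 200) | t = 0.368 (N = 240) |
|---|---|---|
| Stated | 0.0052 / 0.048 | 0.0052 / 0.048 |
| Per side | 0.0015 / 0.0495 | 0.0004 / 0.0498 |
| Applied once | 0.0032 / 0.0487 | 0.0012 / 0.0495 |

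Neither form gives 0.0052/0.048 anywhere in this range.

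**Overall two-sided alpha with 0.0052/0.048** (critical values 2.794 and 1.977)
- Interim crossing counts as rejection: 0.0504 at t = 0.441 and 0.0509 at t = 0.368. Keeping 0.0052 and holding 5% would need a final level of about 0.0476 and 0.0471 respectively.
- Only the final test can reject: 0.0480 at any t, before any effect of sample size re-estimation.

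**Range**
Subjects at the interim may have contributed fewer attacks than they will by the end. Assuming one attack each at the interim, an average of two at the end and an ICC of 0.486, t is about 0.30 to 0.36. At t = 0.30, overall alpha with interim rejection is 0.0513.

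**The case against.** The strongest reply is that the thresholds do no harm. SAP 1.4 has no efficacy stop, protocol 16.3 continues enrolment whatever the interim shows, and no sentence says that p below 0.0052 is a success. If the interim cannot reject, the test at 0.048 is conservative as far as this source goes. Even if it can reject, the excess at 37–44% is under 0.1 percentage point, which is small beside the approximation in a χ² test with an estimated intraclass correlation. This stands, and it limits the point to one of specification. It does not settle the role of the interim test. Table 3 gives that test its own threshold. Protocol 19.6 lists a met primary endpoint among possible grounds for termination, though only in a general list that does not mention 0.0052. The decision flowchart (SAP Figure 1) was not available for this review and may clarify the matter.

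A reader might infer three stronger conclusions.
- *Overall alpha exceeds 5%.* This holds only if an interim crossing counts as rejection. The documents do not say so, and the absence of a stopping criterion argues against it.
- *The pair is the classical boundary and cannot come from a spending function.* The applied-once form gives 0.0052/0.0479 at the protocol's 49% look, so the pair's origin cannot be settled from the documents.
- *The interim threshold is many times too lenient.* The ratio depends on the form: about 3.5 to 12 for the per-side form, and about 1.6 to 4 for the other. It compares nominal p-values and does not measure harm to the error rate.

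**Conclusion.** The point holds as an inconsistency between the stated numbers and the stated method. 0.0052/0.048 fits a look near 50% information. At the SAP's planned look of 44% to 37% of usable subjects, neither common form of the named function yields it. The likeliest explanation is that the thresholds were left unchanged when SAP version 1.1 raised the sample size.

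The size is modest. Depending on the unstated role of the interim test, overall two-sided alpha from this source is either 0.0504 to 0.0509 or 0.048. The trial's validity is not seriously threatened. The reason to act is that pre-specified thresholds for AMSP2 and PF2 should follow from the method named for them.

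The figures assume that information is proportional to usable subjects, that the SAP's 32% loss holds, and that the final N is not chosen from the interim data. The last assumption matters because the interim does re-estimate N. That is a separate mechanism, and its effect cannot be fixed without the rule in Figure 1.

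**What to change.** In SAP 1.4, SAP 1.5.1, SAP Table 3 and protocol 16.3:
- Replace the fixed pair with thresholds computed from the O'Brien-Fleming spending function at the information fraction actually reached. Name the form (0.025 per side, or applied once to two-sided 0.05) and the measure of information (subjects, or attacks allowing for clustering).
- State whether crossing the interim threshold counts as rejecting the null hypothesis for AMSP2 or PF2. If 0.0052 is kept as a rejection threshold, lower the final level to match (about 0.0476 to 0.0471 on the planned figures). If the interim cannot reject, say so and explain why the final test is held at 0.048.
- Reconcile the result with the 5% level in SAP 1.7.1.

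The cost is wording and one standard calculation, with no added patients. Under the named function the final threshold becomes slightly more favourable than 0.048. SAP 1.7.3 commits the sponsor to submit SAP changes to the competent authorities, so the amendment would follow that route. The form of the function should be chosen without reference to interim results.

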### 1.5 Power and sample size calculation

#### 1.5.1 Assumptions

The estimated study size of 200 to 240 included participants has been determined on the basis of data from the pilot study (Fuglsang et al., 2018) and post-market data collected in Denmark, Sweden and Germany from 2018 to 2020.

To estimate the sample size for this trial, it was assumed that 12% of subjects in the sham group and 30% of subjects in the active group would experience PF2. For AMSP2, a 26% response rate in the sham group and a 61% response rate in the active group was assumed.

The primary statistical test for this analysis will be a  $\chi^2$  significance test adjusted for clustered data (using the methods of Donner and Banting (Donner and Banting, 1988)) since subjects could contribute more than one migraine attack. The intraclass correlation coefficient (ICC) from preliminary data on this device was 0.486. This is a group-sequential design with one interim analysis, so the O'Brien Fleming Spending function will be used to set significant thresholds of 0.0052 at the interim analysis and 0.048 at the final analysis.

Power and sample sizes were estimated via simulation using the above parameters for a  $\chi^2$  significance test adjusted for clustered data. These simulations assumed a third of subjects would have one migraine attack during the course of the study, a third of subjects would have two study attacks, and a third of subjects would have three study attacks. In the interim analysis, a more refined method of estimating number of attacks per participant will be employed, using the observed attack frequencies from the interim data (cf. section 1.4). Additionally, it was expected that 22% of subjects would drop out of the trial and 10% of attacks would have missing data at the 2 hour time point, for a total of 32% of randomized subjects that would not provide data usable for the statistical analysis of the primary or secondary endpoint.

#### 1.5.2 Results

The results of the simulations described above are presented in Figure 2 and Table 1 below:

| Total N (dropout inflated) | Total N (excluding dropouts) | PF2 Power | AMSP2 Power |
|----------------------------|------------------------------|-----------|-------------|
| 100                        | 68                           | 54.3%     | 85.2%       |
| 110                        | 76                           | 60.2%     | 90.0%       |
| 120                        | 82                           | 64.1%     | 91.8%       |
| 130                        | 90                           | 67.1%     | 93.8%       |
| 140                        | 96                           | 71.4%     | 95.6%       |
| 150                        | 102                          | 73.7%     | 96.5%       |
| 160                        | 110                          | 76.7%     | 97.1%       |
| 170                        | 116                          | 79.0%     | 97.8%       |
| 180                        | 124                          | 82.2%     | 98.4%       |
| 190                        | 130                          | 83.9%     | 99.0%       |
| 200                        | 136                          | 85.5%     | 99.1%       |

Table 1: Power to detect differences in AMSP2 and PF2 at a given N, assuming 12% sham PF2 response, 30% active PF2 response, 26% sham AMSP2 response, 61% active AMSP2 response, 32% total dropout, and 1-3 attacks per subject

[figure not shown]

Figure 1: Power to detect differences in AMSP2 and PF2 as a function of sample size, assuming 12% sham PF2 response, 30% active PF2 response, 26% sham AMSP2 response, 61% active AMSP2 response, 32% total dropout, and 1-3 attacks per subject

By interpolation of the data in Table 2, it was found that an estimated 200 subjects would be required to achieve over 85% power to detect a difference in PF2 between active and sham groups. This would correspond to greater than 99% power to detect a difference in AMSP2 between groups.

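### SAP Table 1 does not follow from its stated inputs: 136 evaluable patients give about 82% power for PF2, not 85.5%, and the 32% loss adds a patient rate to an attack rate

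*SAP*

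**What the plan says.** SAP 1.5.1 sets out the inputs. For PF2, "it was assumed that 12% of subjects in the sham group and 30% of subjects in the active group would experience PF2". The assumed AMSP2 rates are 26% with sham and 61% with the active device. On clustering, "The intraclass correlation coefficient (ICC) from preliminary data on this device was 0.486"; SAP 1.7.1 defines the quantity used in the test, saying that ρ "is the correlation coefficient between any two responses in the same individual". The error rate is split into "significant thresholds of 0.0052 at the interim analysis and 0.048 at the final analysis". Patients are taken to have one, two or three attacks in equal thirds.

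On losses, SAP 1.5.1 expects 22% of patients to drop out and 10% of attacks to lack the two-hour score, "for a total of 32% of randomized subjects that would not provide data usable" in the endpoint analyses.

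Table 1 in SAP 1.5.2 applies the 32% (200 becomes 136) and gives 85.5% power for PF2 and 99.1% for AMSP2 in that row. Its caption repeats the 32% loss and the range of one to three attacks. The text below it draws the conclusion that "an estimated 200 subjects would be required to achieve over 85% power to detect a difference in PF2 between active and sham groups". The SAP change log (1.1) raises the minimum enrolment from 174 to 200 and the power from 80% to more than 85%.

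**The concern.** Two things look wrong on reading. First, a percentage of patients and a percentage of attacks cannot be added to give a percentage of patients. A retained patient is lost to the analysis only if every one of that patient's attacks lacks a score. Second, the powers in Table 1 do not look attainable from the inputs printed beside them.

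At stake is the stated basis for the new minimum of 200. A reader who tries to verify the power claim cannot do so, and cannot tell which loss model, attack distribution or correlation scale was used. The interim re-estimation in SAP 1.4 projects dropout and attacks per patient separately, so how the two losses combine should be settled before those projections are compared with Table 1.

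**Working it through.** **Inputs.** PF2 12% and 30%; AMSP2 26% and 61%; correlation 0.486 between binary responses; one, two or three attacks in equal thirds; threshold 0.048; losses of 22% (patients) and 10% (attacks), all from SAP 1.5.1. The test is two-sided (SAP 1.7.1: the hypothesis "will be tested using a two-sided adjusted" chi-squared statistic) and allocation is 1:1 (SAP 1.2).

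**Evaluable count.** 200 × (1 − 0.32) = 136. This reproduces the table.

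**PF2 power at 136, by formula.**
- Mean attacks per patient: (1 + 2 + 3)/3 = 2. Mean square: (1 + 4 + 9)/3 = 4.667.
- Design effect: 1 + (4.667/2 − 1) × 0.486 = 1.648.
- Effective attacks per arm: 68 × 2 / 1.648 = 82.5.
- Power = Φ[(0.18 × √82.5 − 1.977 × √(2 × 0.21 × 0.79)) / √(0.30 × 0.70 + 0.12 × 0.88)] = Φ[(1.635 − 1.977 × 0.576)/0.562] = Φ(0.883) = 81.1%.

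The table says 85.5%.

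**AMSP2 power at 68, same formula.** Effective attacks per arm: 34 × 2 / 1.648 = 41.3. Power = Φ[(0.35 × √41.3 − 1.977 × 0.701)/0.656] = Φ(1.31) = 90.6%. The table says 85.2%.

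**Simulation.** 40,000 trials per cell, beta-binomial patients, adjusted chi-squared test with the correlation estimated by ANOVA. The simulation standard error near 82% is √(0.82 × 0.18/40,000), or 0.2 points. All entries are power in %.

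| Randomised / evaluable | PF2 stated | PF2, stated inputs | PF2, two attacks each | PF2, losses in own units | AMSP2 stated | AMSP2, stated inputs | AMSP2, two attacks each | AMSP2, losses in own units |
|---|---|---|---|---|---|---|---|---|
| 100 / 68 | 54.3 | 53.1 | 57.2 | 55.5 | 85.2 | 90.2 | 93.0 | 92.3 |
| 130 / 90 | 67.1 | 64.8 | 69.4 | 67.8 | 93.8 | 96.4 | 97.8 | 97.2 |
| 170 / 116 | 79.0 | 75.7 | 79.6 | 78.6 | 97.8 | 99.0 | 99.5 | 99.3 |
| 200 / 136 | 85.5 | 82.2 | 86.1 | 84.7 | 99.1 | 99.6 | 99.8 | 99.8 |

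On the stated inputs, ten of the eleven PF2 rows in Table 1 are 2.3 to 3.7 points too high. That is a steady offset, not simulation noise. At 136 patients, PF2 power is 82.5% with a threshold of 0.05, 82.5% with unpooled variance, 82.4% with the correlation taken as known, 82.0% with exact thirds, 81.9% when interim rejections are counted, and 82.2% with a mixture model for the clustering. None closes the gap. One-sided testing overshoots, at 88.6%.

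**Losses in their own units.** If attacks are missing independently, a retained patient has no data with probability (0.1 + 0.01 + 0.001)/3 = 3.7%. The share without data is 0.22 + 0.78 × 0.037 = 24.9%, which leaves about 150 of 200. If missingness clusters fully by patient, it is 0.22 + 0.78 × 0.10 = 29.8%, which leaves about 140.

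Power under independent missingness, by formula: 156 patients remain. Mean observed attacks are 0.9 × 2 = 1.8; the mean square is 0.81 × 4.667 + 0.09 × 2 = 3.96; the design effect is 1 + (3.96/1.8 − 1) × 0.486 = 1.583. Effective attacks per arm are 78 × 1.8 / 1.583 = 88.7, and power is Φ(0.990) = 83.9%. Simulation gives 84.5–84.9%. Under full clustering, simulation with 140 patients gives about 83%.

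**The case against.** The strongest reply is that the SAP gives neither its data-generating model nor its number of simulations, so another model might yield 85.5%. Three candidates bring PF2 at 200 within two points of the table: two attacks per patient, as Protocol 16.2 assumes (86.1%); each loss in its own unit (84.7%, with all eleven PF2 rows within two points); and a correlation of 0.486 on a latent scale with the correction fixed at that value (84.4%). The PF2 column may therefore come from a sound simulation with a mislabelled evaluable column. The documents do not settle this.

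That reply stands as an explanation of how the column may have arisen, but it does not rescue the table as printed. The first two candidates depart from the attack distribution or loss that the caption names, and the third from the definition of ρ in SAP 1.7.1. The first two also leave the AMSP2 rows at 100 to 130 randomised unrepaired, and move them further away.

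The same evidence rules out a tempting stronger reading: that the 85% claim survives only because two errors cancel. If attack-level loss was simulated correctly, there may be one labelling error and nothing to cancel.

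A second objection is that the effect is small, and that SAP 1.4 re-estimates the size, up to 240, from observed rates and correlation. This is right about the consequences for the trial. It does not correct the stated figure, which supports the minimum of 200 before any interim data. A third is that the change log gives the reason for 200 simply as more power, and 200 does give more power than 174 under every variant. That also stands; only the stated level is in doubt.

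**Conclusion.** The point holds as a fault of arithmetic and traceability. On the SAP's own inputs, PF2 power at 136 evaluable patients is 81–82%, about 3 to 4 points below the 85.5% stated, and AMSP2 power at 68 is about 90%, about 5 points above the 85.2% stated. The 32% mixes units. With each loss in its own unit, PF2 power at 200 randomised is about 84–85% if attacks are missing independently, and about 83% if missingness clusters fully by patient. The claim of more than 85% thus has no margin.

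A reader might infer that 200 patients are too few. The documents do not support that: primary-endpoint power at 200 exceeds 99% in the table and in every variant shown above, and PF2 falls short by a point or two at most once the losses are applied properly. Nor is 25% the one correct loss; it rests on independent missingness, which the SAP does not state, and the supportable range is about 25–30%.

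The power figures rest on a binary-scale correlation, which follows SAP 1.7.1, and on a beta-binomial model, which is an assumption; a mixture model gives the same 82%.

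**What to change.** In SAP 1.5:
- Re-run both columns of Table 1 with 22% applied to patients and 10% to attacks, using one stated correlation, its scale and one attack distribution. State the data-generating model and the number of simulations.
- Replace the 32% of patients with the resulting share without data (about 25% under independent missingness, up to about 30% under full clustering), say which is assumed, and correct the evaluable column and the caption.
- Restate PF2 power at 200 randomised as about 84–85% (about 82% if only 136 are evaluable), and align the change log.
- Correct the reference in SAP 1.5.2 to interpolation in Table 2. That table lists the secondary hypotheses, and 200 is already a row of Table 1.

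The cost is one re-run of an existing simulation and some restated figures. No extra patients are needed and no analysis changes.
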